The PI developed a web-based intervention (UV4.me) that was found to significantly decrease UV exposure and increase skin protection behaviors among young adults in a randomized controlled trial (RCT) of nearly 1000 participants recruited from a consumer research panel. The intervention (UV4.me) is individually-tailored, interactive, and multimedia in nature, and based on the Integrative Model of Behavioral Prediction. Similar to other online trials, 73% of eligible individuals completed the baseline questionnaire, 70% who were randomized to the intervention accessed it, and 68% accessed it and completed at least one module. However, we have an opportunity to increase the engagement, implementation, and ultimately, the impact of UV4.me. We will do this by adding several key interactive features/strategies suggested by participants, our data, and supported by the literature (i.e., by creating a mobile version, adding incentives embedded in the intervention, a behavior tracking and feedback feature, peer interaction component, and ongoing news updates). This Hybrid Type 2 dissemination-effectiveness project's purpose is to implement the enhanced intervention (UV4.me2) with adults aged 18-25 years at moderate to high risk of developing skin cancer and evaluate the intervention's effectiveness in a sample recruited online through national dissemination to the general population. This project will use the RE-AIM framework to determine the reach, effectiveness, implementation, maintenance, and cost of UV4.me2.

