Reach. We will assess eligibility and enrollment overall and by recruitment source (i.e., skin protection organizations, Google Adwords, Facebook ads, consumer research panel, word of mouth) over 12-18 months in order to assess reach/potential generalizability. Sources will be tracked by placing a unique identifying pixel in each of our authorized web ads so that we know when an individual referred from a pre-specified source accesses the study website. Additionally, we will query participants as to how they found out about the study to identify informal word of mouth diffusion (e.g., unpaid study Facebook page, earned media). The number of individuals who click on the web ads, access the study homepage, complete a screening form, are eligible/ineligible, and use the website without enrolling will be assessed. Organizational sources will be monitored and queried as to strategies (i.e., posting the study URL on their website, additional promotion) used to encourage individual participation. As we have previously, we will use Google Analytics to observe user characteristics and behavior in aggregate in terms of internet source including diffusion via word of mouth, geographic location, technology used (i.e., mobile or not), eligibility/enrollment rates, and so on. We will ask organizations to set up or allow us to set up a Google Analytics "goal" to assess such user characteristics and behavior in terms of individuals accessing the study ad from within the organization's website. We will also query organizations about their number of users/members and website views if they are monitoring these.

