13.0 Statistical Analysis

13.1 Statistical Analyses for Primary Aims

Reach. We will use a one-sample test of a binomial proportion (two-sided, α =0.05) to determine whether the fraction of eligible subjects who enroll and complete the baseline is higher in this project than the prior study. Assuming that 70% of eligible subjects enroll and complete the baseline, we will need access to 2,143 (i.e., 1500/0.70) eligible subjects. Given this sample size, we will be able to detect an increased enrollment and baseline completion proportion with at least 98% power if the true proportion is 70%. Demographic data from enrolled participants will be compared to census data using chi-square goodness of fit tests (two-sided, α =0.05). We will also use the same methods to compare enrollment rates and representativeness separately by recruitment source (i.e., skin protection organizations, Google Adwords, paid Facebook ads, consumer research panel, word of mouth [e.g., unpaid Facebook page, earned media]).

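### Reach by recruitment source rests on separate one-sample tests against a benchmark, which cannot show that sources differ and have low or very uneven power within a source

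*Combined protocol and SAP*

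**What the plan says.** Section 13.1 (Reach) sets out two methods. For enrolment: "We will use a one-sample test of a binomial proportion", two-sided at 0.05, to decide "whether the fraction of eligible subjects who enroll and complete the baseline is higher in this project than the prior study". For representativeness: chi-square goodness-of-fit tests of enrolled participants' demographics against census data, also at 0.05. The sample-size statement is for all sources together: "Assuming that 70% of eligible subjects enroll and complete the baseline, we will need access to 2,143 (i.e., 1500/0.70) eligible subjects", with power of at least 98% at that rate.

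The by-source plan is one sentence: "We will also use the same methods to compare enrollment rates and representativeness separately by recruitment source". It names five sources: skin protection organizations, Google Adwords, paid Facebook ads, the consumer research panel and word of mouth. Section 4.4.1 gives the matching measure: "We will assess eligibility and enrollment overall and by recruitment source".

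For Reach by source the plan gives no test of one source against another, no interval estimate, no expected count and no power.

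Section 13.1 does not state the prior-study rate that serves as the null. Section 1.0 reports that "73% of eligible individuals completed the baseline questionnaire", while section 3.0 puts enrolment with baseline completion at about two thirds.

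**The concern.** A reader of the by-source results will want to know which channels enrol better and which bring in a more representative sample. Five one-sample tests answer a different question, five times: is this source above the prior-study rate, or off the census profile? A significant result in one source and a non-significant one in another is not a test of the difference between them.

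Power was worked out only for the pooled denominator. Each source has a fraction of it, so a source that meets the design assumption exactly may well be reported as showing no improvement, while another with the same rate is reported as improved. Reach is Primary Aim 1, and its by-source part could then suggest channel differences that do not exist, or leave real ones untested.

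**Working it through.** **Inputs.** From section 13.1: one-sample test, two-sided 0.05; design rate p1 = 0.70; 1,500 enrolled; 2,143 eligible. From sections 1.0 and 3.0: prior rate 73% or about two thirds. From section 4.1: five sources. Assumed, because the documents do not give it: the number eligible per source.

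**The plan's own figures.** 1,500 / 0.70 = 2,142.9, so 2,143, as stated. Power for an increase is Φ{[p1 − p0 − 1.96√(p0(1−p0)/n)] / √(p1(1−p1)/n)}. At n = 2,143:
- p0 = 0.66: (0.0400 − 0.0201) / 0.0099 = 2.01, power 97.8% (exact binomial 97.7%). This matches the stated 98%.
- p0 = 2/3: (0.0333 − 0.0200) / 0.0099 = 1.35, power 91%.
- p0 = 0.73: the design rate lies below the null, so power to show an increase is about zero.

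The stated power therefore implies a null near 0.66. That is an inference; section 13.1 does not say so. Both 0.66 and 2/3 are carried below.

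**Per-source rejection probability**, with a true 70% in the source (exact binomial probability that the two-sided 5% z-test rejects):

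| Eligible in source | Share of 2,143 | Null 0.66 | Null 2/3 |
|---|---|---|---|
| 100 | 5% | 11.6% | 11.8% |
| 300 | 14% | 28.8% | 20.8% |
| 429 (equal split) | 20% | 41.1% | 29.4% |
| 1,000 | 47% | 76.6% | 62.4% |
| 1,500 | 70% | 91.6% | 79.3% |

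At 429 the observed rate must reach p0 + 1.96√(p0(1−p0)/429), which is 70.5% (null 0.66) or 71.1% (null 2/3). Both exceed the assumed true rate, so power is below one half. By the normal formula, 80% power needs about 1,080 eligible in one source (null 0.66) or 1,544 (null 2/3), that is 50% or 72% of the total.

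**Mixed verdicts among identical sources.** With an equal split and rejection probability p, the chance that some of the five tests are significant and some are not is 1 − p⁵ − (1−p)⁵.
- p = 0.411: 1 − 0.012 − 0.071 = 92%.
- p = 0.294: 1 − 0.002 − 0.176 = 82%.

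With an assumed split of 1,071 / 429 / 321 / 214 / 107, the same calculation from the five separate probabilities gives 94% and 86%.

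**Same rate, different verdict.** Against 0.66, 700/1,000 (70.0%) gives z = 2.67, p = 0.008; 75/107 (70.1%) gives z = 0.89, p = 0.37.

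**Where the rate matters too.** Against 0.66, an observed 60% or 80% gives z = −4.1 or +9.7 at n = 1,071, and −1.3 or +3.1 at n = 107. Even the small source detects the 80% rate.

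**Representativeness.** The goodness-of-fit statistic grows with n in the same way. For an illustrative 55/45 split tested against 50/50, it is 2n(0.05²/0.5) = 0.01n: p = 0.39 at 75 enrolled and p = 0.006 at 750.

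**What a direct test would offer.** For a 5×2 homogeneity test (4 df, 5%), the noncentrality is λ = Σ nᵢ(pᵢ − p̄)² / [p̄(1−p̄)]. With assumed rates of 65, 67.5, 70, 72.5 and 75% and 429 each, λ = 429 × 0.00625 / 0.21 = 12.8 and power is about 83%. It is about 67% with the unequal split above (largest source at 65%). For a 60–80% spread it exceeds 99% under both splits. When all sources share one rate, the error is 5%.

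**The case against.** The best defence is that no between-source test was clearly promised. Hypothesis 1 concerns enrolment against the prior study and representativeness against the nation; it does not rank sources. Applying the methods separately by source can mean each source against its own benchmark, and each test then answers a legitimate question. Where the plan clearly wants sources compared, it says so, for the implementation measures in sections 4.4.2 and 13.2. This stands as a reading: the word for comparison leaves the Reach sentence ambiguous, and one cannot say that the plan breaks a commitment. The point survives either way. If a between-source comparison is meant, the tests cannot deliver it; if not, five tests without intervals and with low or uneven power still invite the wrong inference.

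A reader might also infer that the by-source results would mainly reflect how many eligible people each source supplied. The documents do not support that. They give no per-source counts and do not say that the sources will be very unequal. With equal sizes, mixed verdicts come from chance, and with widely different rates the rate itself drives the result.

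Nor is the absence of multiplicity control a strong complaint in itself. The by-source tests break down one overall test, and the plan ties no decision to them.

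Finally, one should not replace the census tests with homogeneity tests: sources could agree with each other and all be unrepresentative, which is what Hypothesis 1 asks about.

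**Conclusion.** The point holds in a limited form. The Reach plan contains no analysis that can show a difference between recruitment sources, and its power statement does not carry over to single sources. At the design rate of 70%, a source with one fifth of the eligible people has about 29–41% power, and across the sizes considered the range is about 12% to 92%. Five identical sources would receive mixed verdicts in roughly 82–94% of trials under the two splits examined.

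These figures rest on assumed source sizes, a common true rate of 70% and a null of 0.66 or two thirds. If the null were 73%, a source at 70% would tend to be labelled lower, not higher: with 1,500 eligible, in about 74% of trials. The benchmark tests are not wrong for the benchmark question, and no effectiveness conclusion is affected. This is an inexpensive improvement to the analysis of a primary aim.

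**What to change.** In section 13.1, keep the one-sample enrolment tests and the census goodness-of-fit tests, and add:

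1. Source-specific enrolment rates among eligible people, with 95% confidence intervals.
2. One test of enrolment on the five-level source among all eligible people (logistic regression or a 5×2 homogeneity test, 4 df).
3. For each demographic variable, a source-by-category homogeneity test, with estimated differences between sources and their intervals.
4. A sentence saying that differing per-source p-values are not evidence of differences between sources.

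Also state the prior-study null rate in section 13.1 and reconcile the 73% in section 1.0 with the two thirds in section 3.0, since the pooled power and every per-source result depend on it.

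The cost is wording and a few extra analyses. Section 4.4.1 already plans source tracking and counts of eligible and enrolled people, so no new data are required.

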Efficacy. Skin cancer-related behavioral outcomes will initially be assessed at baseline and 3 months later. They will also be assessed within UV4.me2 via behavioral tracking. We will assess sun protection (e.g., sunscreen use, clothing, shade) and UV exposure (e.g., sunburns, intentional/incidental sun exposure, indoor tanning) using items adapted from Glanz and colleagues and Ingledew and colleagues that our team has cognitively tested and assessed psychometrically with young adults 123-125. Sunburns, indoor tanning, and sunless tanning will be secondary outcomes since engagement in these activities is less frequent than sun exposure and protection in general. Negative effects will be defined as an increase in sunburns. Several studies have demonstrated the reliability and validity of self-report questionnaires of UV exposure and protection compared to observation and objective measures with no systematic bias identified among various populations 126-130. As indicators of quality of life, we will inquire as to the amount of perceived benefits of and barriers to UV exposure and protection 62,131-134.

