Efficacy. We will compare demographics across randomization arms using chi-squares and ANOVAs for categorical and continuous data, respectively. The primary outcomes are baseline to 3-month changes in UV exposure and protection. We will use multivariable linear regression to compare the effectiveness of UV4.me2 with UV4.me, and UV4.me2 with the e-pamphlet. We will not compare UV4.me to the epamphlet because UV4.me compared to a control condition was established in the prior study. Covariates in these models will include study arm, recruitment month/season, US region, and demographic factors identified as significantly imbalanced across arms (confounders). Analyses will be performed separately for the two primary outcomes. Variance stabilizing transformations may be applied as needed. Hypothesis tests will be two-sided with a 1.25% Type I error to account for multiple testing (2 intervention comparisons x 2 outcomes). Based on our data, experience, the enhanced study procedures, and the consumer research panel's experiences with young adults, we anticipate attrition of approximately 20% at each time-point. With 1500 young adults at baseline, we anticipate collecting 3-month follow-up data from 1200 participants, with 240 from the e-pamphlet arm and 480 participants from each of the other arms. The means (SDs) of the baseline to 3-month changes in UV exposure and protection indexes from the prior study control arm were 0.34 (0.74) and -0.37 (0.90), respectively. Given these parameters, we will have 80% power to detect small standardized effect sizes of 0.22 between the UV4.me2 and UV4.me arms, and 0.26 between the UV4.me2 and the e-pamphlet. These correspond to small detectable differences between intervention arms of 0.16 and 0.19 in baseline to 3-month changes in UV exposure and protection indexes, respectively. We will be able to detect slightly larger differences when the UV4.me2 and e-pamphlet arms are compared (detectable differences - UV exposure: 0.20; protection: 0.24). Analyses will assume that missingness depends on observed data (i.e., missing at random; MAR) 141. For drop-outs, the reason for attrition will be analyzed if available to search for evidence of informative missingness. Baseline variables will be compared by whether participants drop out or not. Significant variables will be added to the model to strengthen our MAR assumption. As a sensitivity analysis, we will use a shared parameter model with the assumption of missing not at random 142. If large changes in parameter estimation are found, we will use the results from the shared parameter model.

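### The primary models of 3-month change do not pre-specify the baseline value of the same index as a covariate, which may give up power at no saving

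*Combined protocol and SAP*

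**What the plan says.** Section 13.1 (Efficacy) defines the endpoints: "The primary outcomes are baseline to 3-month changes in UV exposure and protection". Multivariable linear regression compares UV4.me2 with UV4.me and UV4.me2 with the e-pamphlet, separately for the two indexes, at 1.25% two-sided. On covariates it says: "Covariates in these models will include study arm, recruitment month/season, US region, and demographic factors identified as significantly imbalanced across arms (confounders".

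The indexes are behavioural scores, not demographics, so the imbalance rule does not reach them. One other route exists in the same section: "Baseline variables will be compared by whether participants drop out or not", followed by "Significant variables will be added to the model to strengthen our MAR assumption". A baseline index can therefore enter, but only if it turns out to be associated with dropout.

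Three further statements bear on the remedy:
- Section 4.4.1 confirms that the data exist: "Skin cancer-related behavioral outcomes will initially be assessed at baseline and 3 months later".
- Section 13.1 allows transformation: "Variance stabilizing transformations may be applied as needed".
- Section 13.1 allows the missing-data sensitivity model to displace the primary one: "If large changes in parameter estimation are found, we will use the results from the shared parameter model".

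**The concern.** Analysing raw change without the baseline score fixes the slope of the 3-month score on baseline at 1. That is the efficient choice only when the SD ratio times rho equals 1. In all other cases, letting the data estimate the slope gives a smaller residual variance from the same participants.

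The conditional route does not settle this. It selects on whether baseline predicts dropout, whereas the precision gain depends on how baseline relates to the 3-month score. It also leaves the content of the primary model to be decided from the data.

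What is at stake is power for four tests at 1.25%, or equivalently a margin if fewer people complete than planned. Section 13.1 assumes 20% attrition. Section 3.0 reports that about two thirds completed the 3-month follow-up in the prior trial.

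**Working it through.** **Inputs from section 13.1.** Two-sided alpha 0.0125; 80% power; 480, 480 and 240 completers; SDs of change 0.74 (exposure) and 0.90 (protection). The documents do not give rho or k, where k = SD at 3 months / SD at baseline. Both are assumed below.

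**Step 1: reproduce the plan.** z(1 − 0.0125/2) = 2.4977 and z(0.80) = 0.8416, sum 3.3393.
- UV4.me2 vs UV4.me: d = 3.3393 × √(2/480) = 0.2156. In raw units this is 0.160 (× 0.74) and 0.194 (× 0.90).
- UV4.me2 vs e-pamphlet: d = 3.3393 × √(1/480 + 1/240) = 0.2640. In raw units this is 0.195 and 0.238.

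These match the stated 0.22 and 0.26, and 0.16, 0.19, 0.20 and 0.24. The power statement is right for an analysis of change without covariates.

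**Step 2: variance with and without baseline.** Scale the baseline variance to 1. The variance of change is 1 + k² − 2·rho·k. The residual variance after adding baseline, with a common slope, is k²(1 − rho²). Their ratio is

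R = k²(1 − rho²) / (1 + k² − 2·rho·k), and 1 − R = (1 − k·rho)² / (1 + k² − 2·rho·k).

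So R never exceeds 1, and equals 1 only when k·rho = 1.

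**Step 3: power at the same effect.** Power = Φ(3.3393/√R − 2.4977). Completers needed for 80% power = 1,200 × R.

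| k | rho | R | Power with baseline | Completers for 80% |
|---|---|---|---|---|
| 1 | 0.3 | 0.650 | 95.0% | 780 |
| 1 | 0.5 | 0.750 | 91.3% | 900 |
| 1 | 0.7 | 0.850 | 87.0% | 1,020 |
| 1 | 0.9 | 0.950 | 82.3% | 1,140 |
| 1.25 | 0.3 | 0.784 | 89.8% | 941 |
| 1.25 | 0.7 | 0.981 | 80.9% | 1,177 |
| 1.25 | 0.8 | 1.000 | 80.0% | 1,200 |

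Over rho 0.3 to 0.9 and k 1 to 1.5 the gain runs from 0 to 15 points. Outside that range it can be larger: +16.5 points at k = 1, rho 0.2; +18.7 at k = 1, rho 0; +17.8 at k = 1.5, rho 0.95; and +15.3 to +18.7 at k = 0.8, rho 0.3 to 0.8.

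**Step 4: allow for month/season and region.** Suppose these explain a share s of the change variance (assumed), with rho and k now read as conditional on them. Both variances are multiplied by (1 − s).
- s = 0.05: planned model 82.3%. With baseline (k = 1, rho 0.3) 96.0%, a gain of about 14 points.
- s = 0.10: planned model 84.7%. With baseline (k = 1, rho 0.3) 96.9%, a gain of about 12 points.

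**Step 5: checks by simulation.** With 480 per arm and no other covariates, power went from 79.8% to 95.1% (rho 0.3, k 1), from 79.6% to 91.0% (rho 0.5, k 1) and from 80.0% to 79.9% (rho 0.8, k 1.25). With season and region in the model, rejection under the null was 1.1–1.5% with baseline and 1.2–1.5% without, against a nominal 1.25%. The cost of one degree of freedom is negligible: power 0.798773 with 1,191 and 0.798772 with 1,190.

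**Step 6: higher attrition.** If two thirds of 1,500 completed (1,000), the planned test would have Φ(3.3393 × √(1000/1200) − 2.4977) = about 71% power. With baseline and k = 1 it would be about 90%, 85% or 79% at rho 0.3, 0.5 or 0.7. At k = 1.25 and rho 0.8 it would stay at 71%.

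**The case against.** The best defence is that nothing here is wrong. Randomization makes the comparison of change scores valid, the stated power is correct, and the gain may be nil. All of that stands.

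Four further objections have force.

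- **The dropout rule is a real route.** With about 300 dropouts and 1,200 completers, a 5% test (level assumed) has 80% power for a baseline difference of (1.96 + 0.8416) × √(1/300 + 1/1200) = 0.18 SD. So it is inaccurate to say that the plan excludes baseline. It does not pre-specify it.
- **Adjustment is not always at least as precise.** The result in step 2 assumes similar baseline slopes across arms. With a common fitted slope, strongly different true slopes and the 2:1 comparison with the e-pamphlet, precision can fall. Simulated with assumed slopes of 0.5, 0.5 and 1.0 (UV4.me2, UV4.me, e-pamphlet), the variance of that contrast was about 4 to 5% larger with baseline. Those slopes were chosen to show the effect. With 0.6, 0.6 and 0.9, adjustment still won.
- **The shared parameter model is unspecified.** The source cited for it is titled as a mixed effects model for longitudinal responses. If baseline is one of its repeated responses, baseline cannot simply be added as a covariate. The calculations above cover linear regression only.
- **Protection against attrition is protection of power only.** A reader might infer that adjustment also deals with informative dropout. It does not.

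A reader might also infer that the trial is underpowered or its estimate biased, or that 15 points is a ceiling or an expected gain. The documents support none of these. The stated power reproduces, and the gain depends on two quantities that they do not give.

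**Conclusion.** The point holds as one of efficiency. The baseline index is not a pre-specified covariate, and whether it enters depends on a dropout comparison that has little to do with its value for precision. For assumed rho of 0.3 to 0.9 and SD ratio of 1 to 1.5, adding it raises power from 80% by 0 to 15 points before month/season and region. With equal SDs the largest gain in that range becomes about 14 or 12 points if those covariates explain an assumed 5% or 10% of the change variance. That the covariate is not pre-specified is certain; the size of the gain is not. With similar slopes across arms there is no material loss. With strongly different slopes, a loss of a few percent in variance is possible for UV4.me2 vs e-pamphlet. This is an improvement to consider, not a defect that undermines the trial.

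**What to change.** Before outcomes are seen by arm, amend section 13.1 as follows.

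1. Add the baseline value of the same index to each primary linear model, unconditionally.
2. If a variance stabilizing transformation is used, apply it to the baseline and 3-month scores before differencing, and use the transformed baseline as the covariate.
3. State the form of the shared parameter model. If its outcome is change or the 3-month score, condition it on baseline too, so that it matches the model it may replace. If baseline is one of its repeated responses, it already uses the baseline value and no covariate should be added.

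The team could obtain rho and the SD ratio from the prior-trial data that gave the change SDs, and so see the likely gain.

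For the linear models the cost is one or two sentences and one degree of freedom out of about 1,190. No participant is lost, because a change score already requires the baseline value. The sample size need not change.
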